All adverse events volunteered, observed, or solicited will be recorded in the AE CRF from the time the subject signs the informed consent up to and including Week 24. The PI will meet weekly with all study investigators to review the details of data acquisition and analysis as well as any minor problems. AEs will be assessed for each subject at every visit. All adverse events will be recorded and will include the dates of occurrence; severity; assessment of relationship to study drug; countermeasure(s); specific drug therapy used in countermeasure; and outcome. Adverse events will be reviewed by the PI who will complete an adverse event report form and submit this to the IRB within the required time frame in accordance with the IRB guidelines.

Reporting Adverse Events: The PI will report all adverse events experienced by the study subjects in accordance with HRC (Human Research Committee) guidelines to the Institutional Review board. Adverse events will also be reported by the principal investigator to the funding agency and to the FDA in accordance with IND regulations. The reporting of adverse events is the responsibility of the PIs, Drs. [name] and [name].

In case of serious adverse events (SAE's), the PI will report them within 24-hours by telephone, fax or email according to HRC guidelines, followed by a written report within 5 business days. SAEs that occur within 30 days after a subject's last dose of study medication that are categorized as definitely, probably or possibly relate¹d to the study will be reported to the HRC and FDA. An annual report will be submitted to the HRC and the FDA of the progress of the trial. This will include individual study information and information on safety reports from the previous year.

X. REFERENCES

- Johnston, L. D. et al. Monitoring the Future National Survey Results on Drug Use, 1975-2018: Overview, Key Findings on Adolescent Drug Use. (Institute for Social Research, 2019).
- Wang, T. W. *et al.* Tobacco Product Use and Associated Factors Among Middle and High School Students — United States, 2019. *MMWR Surveill. Summ.* 68, 1–22 (2019).
- 3. Barrington-Trimis, J. L. & Leventhal, A. M. Adolescents' Use of 'Pod Mod' E-Cigarettes Urgent Concerns. *The New England journal of medicine* **379**, 1099–1102 (2018).
- 4. Kong, G. & Krishnan-Sarin, S. A call to end the epidemic of adolescent E-cigarette use. *Drug and Alcohol Dependence* **174**, 215–221 (2017).

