Hypothesis 1.6 (secondary): Those assigned to placebo will have a higher rate of cotinine-verified, seven-day point-prevalence nicotine vaping abstinence at end of treatment compared to EUC.

Hypothesis 1.7 (exploratory): Those assigned to varenicline will have an earlier onset of abstinence, longer latency to first lapse, longer latency to relapse, longer duration of abstinence, and greater total number of days of vaping abstinence than those assigned to placebo or EUC as

determined by using data ascertained daily with the emocha Mobile Health app (emocha) or REDCap surveys.

Aim 2 (secondary): To establish the safety and tolerability of varenicline in adolescents attempting to quit vaping nicotine.

Hypothesis 2.1: Nicotine withdrawal symptoms, craving, and negative mood symptoms will be less frequent and severe in the varenicline group than the placebo or EUCgroups.

Hypothesis 2.2: Those assigned to varenicline will have no greater incidence or severity of adverse events (AE) compared with those assigned to placebo or EUC during treatment and follow-up.

Aim 3 (exploratory): To assess if there are between group differences in consumption of alcohol, combusted tobacco, cannabis, and non-medical prescription drugs during the treatment and follow-up periods.

Exploratory Hypothesis: Those assigned to varenicline will have less consumption of alcohol, combusted tobacco, cannabis, and non-medical prescription drugs and greater reduction in severity of nicotine dependence as assessed with the ECDI during the treatment and follow-up periods than those in the placebo or EUC groups.

PILOT STUDY 2020P002774-Pilot - NCT04602494

In 2021, during the national recall of varenicline in the US, the FDA provided temporary authorization for importation of apo-varenicline from the Canadian company, Apotex. A pilot vaping cessation trial was conducted using apo-varenicline or identical placebo in 4 study participants who met inclusion and exclusion criteria below except that the age range was limited to 18-25. In this pilot trial, all study procedures listed below were piloted, including the emocha platform for study medication adherence and daily report of vaping behavior and adverse effects and the novel, brief lay-counselor behavioral vaping cessation intervention.

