Hypothesis 2.1: We will use a linear model applied separately to repeated, continuous weekly assessments of nicotine withdrawal symptoms, craving, and negative mood symptoms. The linear model will be estimated using generalized estimating equations (GEE), providing estimates and standard errors robust to violations of distributional assumptions (e.g., normality), and heteroscedasticity. The model will be applied to the summed scores at each time point per subject. The analysis will be intent-to-treat with missing data imputed per the method specified above. The key confirmatory effect will be a dummy-coded contrast comparing placebo (coded as 0) against varenicline (coded as 1). Exploratory analyses will also be conducted to evaluate varenicline versus EUC and placebo versus EUC. The model will include covariates for a) change over time (two terms encoding linear and quadratic trends), b) baseline levels of the given outcome, as well as c) sex, environment (secondary school versus post-secondary school), and severity of nicotine dependence. Covariates will be standardized (mean-centered and scaled by the standard deviation). P-values will be adjusted to avoid multiple comparison issues using the Benjamini-Hochberg method.

Hypothesis 2.2: We will conduct a Fisher's exact test differences by randomized group in the number (%) of participants who endorse an AE at least once in the 12-week treatment period. We will evaluate frequent AEs (e.g., that occur in at least 5% of the participants at any point between weeks 1 through 12 of the trial).

Sensitivity analyses: We will conduct 3 sensitivity analyses to examine the robustness of our conclusion for efficacy.

- 1. We will test whether our conclusion on efficacy is robust to the inclusion/exclusion of the 3 covariates (biological sex, environment [secondary school vs. post-secondary school], and nicotine dependence severity) we therefore will rerun the analyses without the 3 covariates and examine whether the pooled estimate for the contrasts between varenicline, placebo, and/or EUC changes in sign and significance.
- 2. We will test whether our conclusion on efficacy is robust to the approach for imputation of missing data, examining whether the pooled estimate for the contrasts between varenicline, placebo, and/or EUC changes in sign and significance.
 - a. We will rerun the adjusted (i.e., with covariates) models on the observed data only.

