ii. Nicotine Withdrawal Risks: While it is well known that smoking (and vaping) cessation provides a large overall health benefit to patients, there are potential adverse, though transient, consequences of quitting smoking (and vaping). Many study participants who successfully abstain from nicotine vaping may experience nicotine withdrawal symptoms. Nicotine withdrawal symptoms include anxiety, restlessness, anger, irritability, sadness, difficulty concentrating, increase in appetite, weight gain, difficulty sleeping and craving for tobacco. Withdrawal symptoms begin within a few hours of abstinence, peak 24-48 hours after cessation, and may last up to 4 weeks. Nicotine withdrawal can cause slowing on EEG, decrease in cortisol and catecholamine levels, sleep EEG changes, and a decline in metabolic rate. In adults, the mean heart rate decline is about 8 beats per minute. As with all withdrawal syndromes, the severity varies among subjects. Withdrawal symptoms can also mimic or aggravate the symptoms of other psychiatric disorders or side effects of medications. Participants who are able to quit vaping nicotine are at risk for weight gain. Weight gain following nicotine cessation averages 3-5 kg.

To minimize risk of nicotine withdrawal: Half of participants will receive active varenicline, which will likely diminish withdrawal symptoms. All participants will receive written materials that list withdrawal symptoms that can be expected. Withdrawal symptoms are usually short-lived and never medically dangerous, and most abate after 1-2 weeks.

iii. Psychosocial, Social and Legal Risks: There are no significant psychological, social, or legal risks anticipated with participation in this study. There is a slight risk that the questionnaires and interviews may contribute to temporary discomfort when participants are asked about sensitive behaviors or personal feelings (e.g., drug use, vaping behavior, or mood), but, in our experience with similar studies, this risk is minimal. Participants will be reminded by study staff that they may omit any questions they do not wish to answer or discontinue their participation at any time with no penalty or repercussions. Research staff will provide referral

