The goal of this project is to test whether varenicline, the most effective treatment known for addiction to smoked tobacco, helps adolescent non-smokers who have developed nicotine dependence to quit vaping nicotine. This may benefit other adolescent nicotine vapers in the future and increase abstinence rates in this population by informing clinicians and adolescents who vape and their families of effective treatment options for nicotine vaping cessation. Given the prevalence of vaped nicotine use among adolescents who never smoked is rising more rapidly than any prior known drug, putting them at elevated risk for nicotine dependence, tobacco smoking, other drug use, and direct negative health effects of vaping, we believe that the few potential risks to participants in this research are outweighed by the potential benefits

IX. MONITORING AND QUALITY ASSURANCE

a. Independent monitoring of source data

All data management will be conducted in the offices of the PI at the MGH Center for Addiction Medicine (CAM) in Boston. Standard REDCap data collection forms for all proposed clinical rating scales will be used. Tablets with HIPAA compliant REDCap capability will be used to capture raw data from clinical rating scales entered by participants and study staff and self-reported substance use behavior. A study database will be designed by the PI and the data manager and maintained by the PI, the data manager and the research coordinators. The data manager will review the data weekly. Access to the database is restricted by password. The database will be protected by nightly backup on MGH servers. All data will be stored safely for at least 5 years after study completion.

b. Safety monitoring

An independent Data and Safety Monitoring Board (DSMB) will be appointed for this study, to assess the safety of the study by determining whether there is an unacceptable level of risk due to study medication, study procedures, and whether an increased number of adverse events occur. The DSMB will be established to analyze interim results to assess the safety of the study drug at regular intervals for the duration of the study by determining whether an increased number of adverse events occur among study participants receiving drug compared to participants receiving placebo.

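### The only all-AE test counts participants ever affected; adding a comparison of weekly AEs would show a difference in recurrence that this test cannot see

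*Combined protocol and SAP*

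**What the plan says.** Aim 2 (section II) concerns safety and tolerability. Hypothesis 2.2 predicts that participants on varenicline will have "no greater incidence or severity of adverse events (AE) compared with those assigned to placebo or EUC during treatment and follow-up".

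The analysis is in section VI under Hypothesis 2.2: a Fisher's exact test by randomised group on the "number (%) of participants who endorse an AE at least once in the 12-week treatment period". The plan also evaluates frequent AEs, for example those "that occur in at least 5% of the participants at any point between weeks 1 through 12 of the trial", but states no method for that.

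The data are richer than this endpoint. Section V.f has AEs assessed weekly in the treatment phase and monthly afterwards. Section IX.d says "AEs will be assessed for each subject at every visit" and "All adverse events volunteered, observed, or solicited will be recorded in the AE CRF", with dates of occurrence and severity for each event.

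Oversight is described separately. Section IX.b asks the DSMB to determine at interim reviews "whether an increased number of adverse events occur among study participants receiving drug compared to participants receiving placebo". Section IX.c sets a comparison of serious AEs, active against placebo, at a two-tailed p value below 0.05, which triggers a discussion about stopping.

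**The concern.** The Fisher endpoint reduces up to 12 weekly reports to one yes or no. A participant with nausea on one day scores the same as a participant with nausea in every week. The section specifies no event count, event rate, recurrence or duration analysis, although the dates needed for one are collected.

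The direction of the hypothesis makes this matter. Hypothesis 2.2 predicts no excess on varenicline, so a non-significant result is likely to be read as support for it. A test that cannot respond to repeated events therefore leans towards the favourable conclusion. Tolerability over a 12-week course depends on how persistent AEs are, as well as on whether one ever occurred.

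**Working it through.** The documents state no AE rate and no power figure for safety, so there is nothing to reproduce. The checks below use the plan's design figures and assumed rates.

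**Inputs from the documents.** Up to 240 are randomised (section II) in a 1:1:1 ratio (section IV.c), so 240 / 3 = 80 per arm. There are 12 weekly AE checks (section V.f).

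**Assumptions.** Two-sided alpha of 0.05 (none is stated for Hypothesis 2.2), no dropout unless noted, and the AE rates shown.

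**Step 1: excess in repeat events only.** Suppose the same share is affected in each arm, but affected participants average 1.5 events on placebo and 3 on varenicline. With 30% affected, the means are 0.30 × 1.5 = 0.45 and 0.30 × 3 = 0.90 events per participant. Simulated rejection rates:

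| Share affected, both arms | Fisher | Robust test on AE counts |
|---|---|---|
| 30% | 4% | 69% |
| 60% | 3% | 99% |
| 90% | 3% | 100% |

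Fisher stays at its false-positive rate whatever the share affected. This result needs no ceiling.

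**Step 2: raised weekly risk throughout treatment.** Each participant has 12 yes/no weeks with a normal random intercept on the logit scale and a constant conditional odds ratio of 2. The comparison is Fisher on ever/never against a robust z-test on the share of weeks with an AE.

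| Weekly AE, placebo v varenicline | Random-intercept SD | Fisher power | Weekly-AE power |
|---|---|---|---|
| 2% v 4% | 1 | 37% | 52% |
| 5% v 9% | 1 | 52% | 76% |
| 10% v 17% | 1 | 55% | 87% |
| 20% v 31% | 1 | 41% | 93% |
| 30% v 43% | 1 | 24% | 95% |
| 5% v 9% | 1.5 | 35% | 50% |
| 20% v 29% | 1.5 | 33% | 70% |

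Repeat simulations moved these figures by a few points. Type I error was about 3% for Fisher and 4-6% for the weekly test, so the gap is not bought with false positives. The share ever affected is 38% v 56% in the 5% v 9% row with SD 1, well short of a ceiling, and 80% v 91% in the 20% v 31% row.

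**Step 3: when a ceiling would arise.** If weeks are independent with weekly probability p, the share ever affected is 1 − (1 − p)^12. This gives 46% at p = 5%, 72% at 10%, 86% at 15% and 93% at 20%. If events cluster in some participants (gamma frailty, shape 0.5), even 0.30 events per week gives only 1 − (1 + 12 × 0.30 / 0.5)^(−0.5) = 65%. Saturation therefore needs a high weekly rate with little clustering.

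**Step 4: cases that favour Fisher.**
- *Rare AE type.* With 0.01 events per week on placebo and a rate ratio of 2, 11% v 21% are ever affected. Power is 33% for Fisher and 41% for a count test.
- *Early excess only.* With 5% weekly on placebo, odds ratio 10 in weeks 1-2 only and SD 1.5, Fisher is slightly ahead (52% v 47%). With odds ratio 6 and SD 1 it is behind (39% v 52%).
- *Dropout after AEs.* With 10% weekly on placebo, a constant odds ratio of 2 and a 20% chance of leaving after each AE week on varenicline only, the weekly test still leads (70% v 50%). Its own power falls from 91% to 70%, and its estimated excess from 8.8 to 6.5 percentage points.

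**The case against.** The strongest reply is that the number of participants affected is a standard reading of incidence, so the Fisher test answers that part of Hypothesis 2.2. This stands, and it is why the test should stay.

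A reader might infer that the plan sets one safety question and then tests another, because section IX.b speaks of the number of AEs. That wording is the DSMB's interim remit and not the hypothesis. The DSMB also receives a description of all AEs, and serious AEs have their own comparison. So Fisher is the only all-AE test in the statistical section, but not the only safety comparison in the trial.

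A reader might also infer that nearly everyone will report an AE and the arms will converge at a ceiling. Section VII.ii does not support this. It says "Many study participants who successfully abstain from nicotine vaping may experience nicotine withdrawal symptoms", which is conditional on abstaining and says only that symptoms may occur. Nothing says withdrawal symptoms are coded as AEs. Withdrawal, craving and mood already have a repeated-measures GEE under Hypothesis 2.1.

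Finally, a constant odds ratio over 12 weeks with no dropout favours the weekly measure. Section VII.i reports that AEs in the adolescent pharmacokinetic studies resolved during the study, and participants may leave because of AEs. This also stands. An early, short-lived excess can remove the gain, and the weekly measure under-weights those who leave. These are reasons to report both measures, not reasons to omit recurrence.

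**Conclusion.** The concern holds in a limited form. The planned test is valid for the proportion affected, but it ignores recurrence and duration and could miss a higher AE burden on varenicline. No such excess is shown, and whether one would in fact be missed depends on AE rates that the documents do not give.

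Under the constant-effect model with SD 1 and placebo weekly rates of 5-30%, Fisher has about 22-56% power against about 76-95% for a robust test on weekly AEs. The loss comes from reducing 12 reports to one, and a ceiling adds to it only at high weekly any-AE rates. The primary efficacy result is unaffected. The addition is worth making but does not replace the Fisher test.

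Hypothesis 2.2 also names severity and the follow-up period. Neither the Fisher test nor the added comparison covers these.

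**What to change.** Keep the Fisher ever/never comparison in Hypothesis 2.2. Beside it, add a varenicline-placebo comparison of the proportion of weekly checks (weeks 1-12) with an AE, for any AE and for each frequent AE. Fit it by GEE with a binary outcome, participant as the cluster and robust standard errors, and report the difference with its 95% CI. Give the DSMB the same summary by arm, so that its question about the number of AEs has a defined measure.

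The cost is one paragraph in section VI and a few lines of code. The GEE software is already named for Hypothesis 2.1, and no new data are needed. The downside is a second safety measure that can under-weight participants who leave because of AEs. The ever/never comparison stays beside it because it still counts them.
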